## **6 EXPECTED TOXICITIES AND DOSING DELAYS/MODIFICATIONS**

Dose delays and modifications will be made using the following recommendations. Toxicity assessments will be done using the NCI Common Terminology Criteria for Adverse Events (CTCAE v4.0) which is identified and located on the CTEP website at:

<http://ctep.cancer.gov/reporting//ctc.html>).

If possible, symptoms should be managed symptomatically. In the case of toxicity, appropriate medical treatment should be used (including anti-emetics, anti-diarrheals, etc.).

All adverse events experienced by participants will be collected from the time of the first dose of study treatment, through the study and until the final study visit. Participants continuing to experience toxicity at the off study visit may be contacted for additional assessments until the toxicity has resolved or is deemed irreversible.

Grade 3 or 4 toxicities that are due to biliary ductal dilatation and resolved with placement of a biliary stent or with biliary stent change will not require a dose reduction of FOLFIRINOX, capecitabine, proton radiation therapy or Losartan after stent placement. Therapy may be withheld for procedures like repeat ERCP, and restarted at the treating physician's discretion per standard of care.

### **6.1 Anticipated Toxicities**

A list of the adverse events and potential risks associated with the agents administered in this study appear below and will determine whether dose delays and modifications will be made or whether the event requires expedited reporting **in addition** to routine reporting.

#### **6.1.1 FOLFIRINOX Therapy**

### 6.1.1.1 Anticipated Hematologic adverse events

Below is the table of adverse events associated with the FOLFIRINOX regimen in the Prodiges-4/ACCORD trial in patients with advanced pancreatic adenocarcinoma (based on ASCO 2010 presentation).

AE, % per patient	Folfinorox N=167	
	All	Grade 3/4
Neutropenia	79.9	45.7
Febrile Neutropenia	7.2	
Anemia	90.4	7.8
Thrombocytopenia	75.2	9.1

### 6.1.1.2 Anticipated Non-Hematologic adverse events

Below is the table of non-hematologic adverse events associated with the FOLFIRINOX regimen in the Prodiges-4/ACCORD trial in patients with advanced pancreatic adenocarcinoma.

AE, % per patient	Folfinorox N=167	
	All	Grade 3/4
Infection without neutropenia	6	1.2
Peripheral neuropathy	70.5	9
Vomiting	61.4	14.5
Fatigue	87.3	23.2
Diarrhea	73.3	12.7
Alopecia (grade 2)	32.5	(11.4)
ALT	64.8	7.3

#### 6.1.2 5-Fluorouracil Anticipated Toxicities

Nausea, diarrhea, taste alteration, vomiting (mild); stomatitis: 5–8 days after treatment initiation; myelosuppression: granulocytopenia (9–14 days); thrombocytopenia (7–14 days); Alopecia; loss of nails; hyperpigmentation; photosensitivity; Maculopapular rash; palmar–plantar erythrodysesthesias: (42–82% receiving continuous infusion); CNS effects: cerebral ataxia (rare); Cardiotoxicity: MI, angina; asymptomatic S–T changes 68%; ocular effects: excessive lacrimation and less commonly, tear duct stenosis.

#### 6.1.3 Irinotecan Anticipated Toxicities

Virtually all phase I and II studies of irinotecan have reported neutropenia and/or late diarrhea (diarrhea occurring more than 24 hours after irinotecan administration) as the dose-limiting toxicities (depending upon the schedule). Other commonly observed adverse events include nausea and vomiting, anorexia, abdominal cramping, alopecia, asthenia, lymphocytopenia, and anemia. Dehydration has occurred as a consequence of diarrhea, particularly when associated with severe vomiting. Patients may have an acute syndrome of lacrimation, diaphoresis, abdominal cramping, and diarrhea (early diarrhea) during or shortly after irinotecan administration; this syndrome is thought to be cholinergically mediated and may be treated and subsequently prevented with atropine. Sporadic cases of pulmonary toxicity, manifested as shortness of breath, nonproductive cough, and transient infiltrates on chest X-ray have been reported. Infrequent occurrences of mucositis or colitis (sometimes with gastrointestinal bleeding) have been observed. Occasionally, abnormalities of serum creatinine, hepatic enzymes, or thrombocytopenia have been observed. Further information regarding irinotecan may be obtained from the package insert.

#### 6.1.4 Oxaliplatin Anticipated Toxicities

The most commonly observed oxaliplatin toxicities include neurotoxicity, GI toxicity, and myelosuppression. Three neurotoxicity syndromes have been seen: acute sensory neuropathy develops within hours to 2 days after oxaliplatin administration. Symptoms include, paresthesias, dysesthesias, and hypoesthesia of the hands, feet and perioral region. Jaw spasm,

abnormal tongue sensation, dyarthria, eye pain and a sensation of chest pressure have also been noted. Acute sensory neuropathy symptoms may be exacerbated by exposure to cold temperature or cold objects. Symptoms are reversible, usually resolving within 14 days and commonly recurring with further dosing. This syndrome has been observed in about 56% of patients receiving oxaliplatin with 5-FU and leucovorin. Acute pharyngolaryngeal dysesthesia is reported to occur in 1-2% of patients. This syndrome is characterized by a subjective sensation of difficulty breathing or swallowing without laryngospasm or bronchospasm or objective evidence of hypoxia. Avoidance of cold drinks, food and air is suggested in order to minimize pharyngolaryngeal dysesthesia. Antianxiety agents (e.g. lorazepam) may be used to treat pharyngolaryngeal dysesthesias once oxygen saturation has been documented to be normal. Peripheral neuropathy persisting > 14 days is characterized by paresthesias, dysesthesias, and hypoesthesia. Abnormalities in proprioception may also be seen. Symptoms of persistent neuropathy may improve upon discontinuation of oxaliplatin. Various agents have been used in an attempt to minimize neurotoxicity of oxaliplatin (e.g. carbamazepine, Mg+, Ca++). Calcium and magnesium infusions appear to be beneficial in preventing neurotoxicity. Gastrointestinal toxicities include nausea, vomiting (oxaliplatin is considered to be moderately emetogenic) and diarrhea. Neutropenia is reported in 73% of patients receiving oxaliplatin with 5-FU and leucovorin (44% grade 3 or 4). Grade 3 or 4 thrombocytopenia is reported to occur in 4% of patients receiving the combination. Allergic reactions, similar to those seen with other platinum compounds, have also been observed in patients treated with oxaliplatin. Reactions range from rash to anaphylaxis. Rarely, oxaliplatin has been associated with pulmonary fibrosis, which may be fatal. Oxaliplatin should be discontinued in the presence of unexplained pulmonary symptoms (e.g. nonproductive cough, dysphagia) or pulmonary infiltrates until interstitial lung disease or pulmonary fibrosis have been ruled out. Recent reports of oxaliplatin extravasation suggest that tissue necrosis may result and that oxaliplatin should be considered a vesicant. No standard treatment exists for oxaliplatin extravasation although heat and sodium thiosulfate have both been suggested. Veno-occlusive disease (VOD) of the liver is a rare complication associated with oxaliplatin and 5-FU. Clinical manifestations of VOD include hepato-megaly, ascites, and jaundice. Histologically, VOD is characterized by diffuse damage in the centrilobular zone of the liver. Sequelae of VOD include hepatomegaly, splenomegaly, portal hypertension, and esophageal varices. A recent analysis of resected liver metastases in 153

patients indicated histological findings consistent with VOD in 6/27 patients who received 5-FU alone, 4/17 patients who received 5-FU and irinotecan, 20/27 patients who received 5-FU and oxaliplatin, and 14/16 who received 5-FU, oxaliplatin and irinotecan. The remaining 66 patients had not received chemotherapy prior to resection. There were no such findings in these patients. For more information on toxicities associated with oxaliplatin, please see the package insert.

#### 6.1.5 Leucovorin: Anticipated Toxicities

6.1.6 The only adverse reactions associated with leucovorin are allergic reactions. These are extremely uncommon.

Radiation Therapy  
The most common toxicities of radiation therapy are fatigue, nausea, abdominal pain, diarrhea, indigestion, vomiting, weight loss and anorexia. Other toxicities may include radiation fibrosis if surgery is delayed too long. Much less common toxicities could include liver damage, kidney damage, and late second malignancies.

#### 6.1.7 Capecitabine

The most common toxicities of capecitabine are diarrhea, indigestion, nausea, vomiting, weight loss, anorexia, and hand-foot syndrome (skin changes and tenderness of hands and feet, especially fingers and toes). Other toxicities may include neutropenia, thrombocytopenia, anemia, cutaneous eruptions, alopecia, fever, and fatigue or general malaise. Much less common toxicities could include allergic reactions and coronary vasospasm.

Patients with moderate renal impairment as measured by serum creatinine ( $> 1.3$ ) at baseline require dose reduction.

#### 6.1.8 Losartan

Common and anticipated toxicity related to Losartan is an adverse effect on blood pressure (hypotension) and potential for electrolyte imbalance such as hyperkalemia.

#### ***Toxicity (Greater than 1%)***

**Hypotension:** Symptomatic first dose hypotension was noted following a 100 mg oral dose, leading to drug discontinuation during a dose finding clinical study (Goldberg et al, 1995b). The incidence appears to be dose-related, increasing from less than 0.5% at doses of 50 mg daily or less, to 2.2% at doses of 100 mg daily (Ellis & Patterson, 1996a).

**Hyperkalemia** Hyperkalemia has been reported during the postmarketing use of losartan (Prod Info Cozaar(R) , 2005). In hypertensive patients with non-diabetic, chronic renal disease, serum potassium was increased significantly to 4.6 mmol/L (mmol/L) from baseline (4.23 mmol/L) during dosing with 100 mg losartan daily, but not with a lower 50 mg daily dose (Gansevoort et al, 1994a). During fixed-dose treatment with losartan 50 mg plus hydrochlorothiazide 12.5 mg in over 200 patients, 11% of patients had changes upward or downward in serum potassium of at least 0.5 mEq/L after 12 weeks (Critchley et al, 1996b). Among 112 hypertensive patients with mild-to-severe renal failure (including 28 on hemodialysis) followed for 12 weeks during losartan treatment, 8% to 18% experienced decreased serum potassium levels greater than 0.5 mEq/L, while 15% to 23% experienced increases greater than 0.5 mEq/L. One patient was withdrawn due to hyperkalemia to greater than 6 mEq/L (Toto et al, 1998).

### **Hyponatremia**

Hyponatremia has been reported during the postmarketing use of losartan (Prod Info Cozaar(R) , 2005).

### **Gastrointestinal tract findings**

Diarrhea (2.4%) and dyspepsia (1.3%) were the most common gastrointestinal side effects, reported more frequently in losartan patients than those treated with placebo (Prod Info Cozaar(R), 2002a).

### **Musculoskeletal findings**

Back pain, leg pain, muscle cramps, and myalgia were reported in between 1% and 1.8% of patients on losartan monotherapy, and had frequency rates greater than comparable placebo-treated patients (Prod Info Cozaar(R), 2002a). Although no direct causal relationship can be established, the events reported in 2 or more patients but less than 1% of patients in clinical

trials included arm pain, hip pain, joint swelling, knee pain, shoulder pain, stiffness, arthralgia, arthritis, fibromyalgia, muscle weakness, and generalized musculoskeletal pain (Prod Info Cozaar(R), 2002a).

### **Asthenia**

Incidence: 1% or greater (Prod Info COZAAR(R) oral tablets, 2008). Asthenia occurred in 1% or greater of patients receiving losartan potassium treatment compared with patients receiving placebo during clinical studies (Prod Info COZAAR(R) oral tablets, 2008).

### **Dizziness**

Incidence: 3% (Prod Info COZAAR(R) oral tablets, 2008). Dizziness occurred in 3% of patients (n=1075) receiving losartan potassium treatment compared with 2% of patients (n=334) receiving placebo during clinical studies (Prod Info COZAAR(R) oral tablets, 2008)

### **Insomnia**

Incidence: 1% or greater (Prod Info COZAAR(R) oral tablets, 2008). Insomnia occurred in 1% or greater of patients receiving losartan potassium treatment compared with patients receiving placebo during clinical studies (Prod Info COZAAR(R) oral tablets, 2008).

### **Cough**

The incidence of cough in clinical trials with losartan monotherapy was 3.4%, with the placebo-treatment group reporting an incidence of 3.3% (Prod Info Cozaar(R), 2002a). Results from controlled phase III clinical trials suggest that losartan may not produce the cough associated with angiotensin-converting enzyme (ACE) inhibitors (Anon, 1994; Karlberg, 1993a). Preliminary results from a multicenter trial to investigate the incidence of losartan induced cough in patients with a history of ACE-inhibitor (lisinopril) cough support this contention (Anon, 1995; Lacourciere et al, 1994). In comparative trials involving nearly 300 patients using fixed-dose losartan 50 mg plus hydrochlorothiazide, cough was seen exclusively in patients over 65 years old, with a frequency of 2.1%. In this age group, cough was nearly 5-fold more frequent (9.8%) among patients treated with fixed-dose captopril plus hydrochlorothiazide (Critchley et al, 1996b). Additionally, losartan 25 mg induced dry cough in 2 elderly diabetic women (age 73- and 80-years-old), who stopped lisinopril therapy due to cough. Two weeks after discontinuing losartan, symptoms of cough were resolved (Conigliaro, 1999).

### **Respiratory finding**

Upper respiratory infection (7.9%) was the most common adverse effect overall in clinical trials with losartan monotherapy, although the placebo-treatment frequency was 6.9% (Prod Info Cozaar(R), 2002a). Other events with frequencies greater in losartan patients included nasal congestion (2%), sinus disorders (1.5%), and sinusitis (1%) (Prod Info Cozaar(R), 2002a).

## **6.2 Toxicity Management**

### 6.2.1 FOLFIRINOX therapy

6.2.2 “One cycle” will constitute one administration of FOLFIRINOX therapy, administered on Day 1-3. Each cycle will be 14 days long +3/-1 days at physician discretion, unless further dose delay is warranted by toxicities. Cycles of FOLFIRINOX administration will be repeated every 14 days. The table below indicates potential dose levels for each of the agents for which dose modifications will be allowed. Dose adjustments of each agent may be made independently based on the specific types of toxicities observed All dose reductions are to be made at the discretion of the treating medical oncologist.

Patients who require multiple dose reductions for grade 2 toxicity may, at the physician’s discretion, begin the following cycle at one dose level higher than the current dose reduction. If dose reduction beyond –3 for any agent is required, that agent should be discontinued.

Agent*	Oxaliplatin	Irinotecan	5-FU Bolus	5-FU Continuous Infusion
Initial Dose	85 mg/m 	180 mg/m 	400 mg/m 	2400 mg/m  per 46-48 hours
Level –1	65 mg/m 	150 mg/m 	320 mg/m 	1920 mg/m  per 46-48 hrs

Level –2	50 mg/m 	120 mg/m 	270 mg/m 	1600 mg/m  per 46-48 hrs
Level –3	40 mg/m 	100 mg/m 	230 mg/m 	1360 mg/m  per 46-48 hrs

Leucovorin dose is always 400 mg/m^2, IV given prior to bolus 5-FU. If any bolus 5-FU is to be skipped, leucovorin can be omitted or alternately can be dose-reduced and given with continuous infusion 5-FU at the discretion of the treating physician.

### 6.2.2.1 Hematologic toxicities

The following dose modifications are based on toxicity demonstrated during a mid-cycle visit and/or at the time of laboratory assessment for planned administration of the next cycle of therapy (for example on the planned day of administration of Cycle 2 Day 1 after completing the 14-day period constituting Cycle 1.) As the Grade 2-4 neutropenia rate in the PRODIGE-ACCORD trial was 79.9%, in this trial prophylactic Neulasta (Pegfilgrastim) 6mg SC x1 will be administered 24-48 hours after discontinuation of continuous infusion 5-FU as clinically indicated per institutional standard of care.

#### Dose Reduction Table for Hematologic Toxicity

(Note: DR = Dose Reduction)

Hematologic Toxicity on the Day of Treatment (D1)	Action	Oxaliplatin	Irinotecan	5-FU Bolus (Leucovorin follows protocol for 5FU bolus)	5-FU Continuous Infusion
Neutropenia G2 (ANC 1500-1000) – all patients should have Neulasta support per institutional guidelines	HOLD ALL THERAPY	Hold until ANC $\geq$ 1500, resume without dose reduction	Hold until ANC $\geq$ 1500, resume without dose reduction	Hold until ANC $\geq$ 1500, resume without dose reduction	Hold until ANC $\geq$ 1500, resume without dose reduction
Neutropenia G3-4, Febrile neutropenia	HOLD ALL THERAPY, Supportive care and	Hold until ANC $\geq$ 1500, resume @	Hold until ANC $\geq$ 1500, resume @	Hold until ANC $\geq$ 1500, resume @	Hold until ANC $\geq$ 1500, resume @

(ANC 1000-500, <500)	antibiotics per institutional guidelines	permanent DL-1 level once resolved	permanent DL-1 level once resolved	permanent DL-1 level once resolved	permanent DL-1 level once resolved
Thrombocytopenia G1 (LLN – 75K)	Treat with DR Oxaliplatin	Treat at permanent DL -1	No reduction	No reduction	No reduction
Thrombocytopenia G2 (75K – 50K)	HOLD ALL THERAPY	Hold until resolved to >100K, resume at permanent DL-1	Hold until resolved to >100K, no reduction	Hold until resolved to >100K, No reduction	Hold until resolved to >100K, No reduction
Thrombocytopenia G3-4 (50K – 25K, <25K)	HOLD ALL THERAPY	Hold until resolved to >100K. Resume @ permanent DL-1 if resolved in 1 wk, permanent DL -2 if >1 wk to resolve	Hold until resolved to >100K. Resume @ permanent DL-1.	Hold until resolved to >100K	Hold until resolved to >100K

### 6.2.2.2 Gastrointestinal toxicities:

Lacrimation, rhinorrhea, miosis, diaphoresis, hot flashes, flushing, abdominal cramping, diarrhea, or other symptoms of early cholinergic syndrome may occur during or shortly after receiving irinotecan. Atropine, 0.25-1.0 mg IV or SC may be used to treat these symptoms. In patients with troublesome or recurrent symptoms, prophylactic administration of atropine shortly before irinotecan therapy may be considered. Additional antidiarrheal measures may be used at the discretion of the treating physician. Anticholinergics should be used with caution in patients with potential contraindications (e.g., obstructive uropathy, glaucoma, tachycardia, etc.)

Late diarrhea (e.g., developing more than 24 hours after irinotecan) should be managed with loperamide. The following dose modifications are based on toxicity experienced during a cycle (i.e., after Day 1 of any cycle).

Dose Reduction Table for Non-Hematologic Toxicity (Except Neuropathy)

(Note: DR = Dose Reduction)

Non-hematologic Toxicity on the Day of Treatment (D1)	Action	Oxaliplatin	Irinotecan	5-FU Bolus (Leucovorin DR follows protocol for 5FU bolus DR)	5-FU Continuous Infusion
Diarrhea G2	DR Irinotecan Bolus 5FU, and CI 5FU	No reduction	Treat at permanent DL -1	Treat at permanent DL -1	Treat at permanent DL -1
Diarrhea G 3-4	DR Irinotecan and CI 5FU and eliminate Bolus 5FU	No reduction	Treat at permanent DL -1	Permanently eliminate bolus	Treat at permanent DL -1
Mucositis G2	DR Bolus and CI 5FU	No reduction	No reduction	Treat at permanent DL -1	Treat at permanent DL -1
Mucositis G3-4	DR Irinotecan and CI 5FU, eliminate Bolus 5FU	No reduction	Treat at permanent DL -1	Permanently eliminate bolus	Treat at permanent DL -1
Nausea/Vomiting G3-4	HOLD ALL THERAPY	Maximal antiemetic therapy. Hold until resolved to G2 or less, resume @ permanent DL-1	Maximal antiemetic therapy. Hold until resolved to G2 or less, resume @ permanent DL-1	Maximal antiemetic therapy. Hold until resolved to G2 or less, resume @ permanent DL-1	Maximal antiemetic therapy. Hold until resolved to G2 or less, resume @ permanent DL-1

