### 2.1.3 Irinotecan

Irinotecan is a camptothecin topoisomerase I inhibitor commonly used in gastrointestinal malignancies. In the FOLFIRINOX regimen it is delivered as a 180 mg/m^2 infusion over 90 minutes on Day 1 of treatment. Diarrhea and neutropenia are the major dose-limiting toxicities of irinotecan. Diarrhea can occur either acutely (within the first 24 hours) and delayed (after 2-4 days.) Acute diarrhea is thought to be mediated by non-competitive inhibition of acetyl cholinesterase activity by irinotecan, and is readily treatable with atropine, 0.25-1 mg, intravenously. Delayed diarrhea often manifests after the second or third weekly dose of

irinotecan, and is thought to be secretory in nature, resulting from abnormal intestinal ion transport. Anti-diarrheal agents, such as loperamide, diphenoxylateatropine (Lomotil®), octreotide, scopolamine and bismuth are typically ineffective once grade IV diarrhea has occurred. The diarrhea usually lasts 5-7 days before resolving. Early recognition of diarrhea and prompt institution of an intensive and prolonged course of loperamide appears to be the most effective approach to this problem. Myelosuppression is manifested primarily as leukopenia and neutropenia. Other toxicities include nausea, vomiting, alopecia and cumulative fatigue or asthenia. Instances of possible drug related hepatic toxicity have occurred, but are rare.

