#### **6.2.3 Capecitabine and Radiation**

Hematologic and Non-Hematologic Toxicity

Capecitabine will be held for any Grade 3 or 4 toxicity. After toxicity resolves to  $\leq$  grade 1, capecitabine will be resumed at 600 mg/m^2 BID to complete the 10 weekdays of therapy.

Capecitabine can be held a maximum of 7 days. If further grade 3 or 4 toxicity is noted at the

reduced dose level, after toxicity resolves to  $\leq$  grade 1, capecitabine will be resumed at 500 mg/m^2 BID to complete two weeks of therapy. If the second dose reduction is not tolerated, capecitabine will be stopped. Patients will keep a capecitabine diary and will record the number of capecitabine tablets and the time that they take the tablets.

Radiation therapy will be held for Grade 3 or 4 nausea that is not well controlled with antiemetic support, until nausea resolves to Grade 2 or less. It will then be resumed at same dose.

Grade 3 or 4 toxicities that are due to biliary ductal dilatation and resolved with placement of a biliary stent or with biliary stent change will not require a dose reduction of capecitabine or radiation therapy after stent placement. Therapy may be withheld for procedures like ERCP and biliary stenting, and restarted at the treating physician's discretion.

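### The non-hematologic dose-reduction table names two different times for grading toxicity, and its grade 3-4 diarrhea and mucositis rows give no hold or recovery grade before re-treatment

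*Combined protocol and SAP*

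**What the plan says.** Section 6.2.2.2 introduces its table of non-hematologic dose reductions (neuropathy excepted) with this sentence: "The following dose modifications are based on toxicity experienced during a cycle (i.e., after Day 1 of any cycle". The first column of that table is headed "Non-hematologic Toxicity on the Day of Treatment (D1".

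The table has three grade 3-4 rows:

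- **Diarrhea.** The action is "DR Irinotecan and CI 5FU and eliminate Bolus 5FU". Irinotecan and infusional 5-FU each carry "Treat at permanent DL -1", the bolus is permanently removed, and oxaliplatin is not reduced.
- **Mucositis.** The action is "DR Irinotecan and CI 5FU, eliminate Bolus 5FU", with the same four drug entries.
- **Nausea/vomiting.** All therapy is held, and each drug carries "Hold until resolved to G2 or less, resume @ permanent DL-1".

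Three general provisions surround the table. Section 6 describes its dose rules as recommendations. Section 6.2.2 (FOLFIRINOX) lets a cycle be delayed beyond its window when toxicity warrants, and it leaves dose reductions to the treating oncologist.

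**The concern.** The introductory sentence and the column heading answer the same question differently: which toxicity sets the next dose? The sentence counts what happened during the cycle just finished. The heading counts what is present when the patient arrives for treatment. A clinician who works from the table alone could grade only that day's symptoms and repeat full doses after a severe episode that has cleared.

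The second problem does not depend on which reading is chosen. A patient who still has grade 3-4 diarrhea or mucositis on Day 1 falls in a row that says to treat at a lower dose, with no instruction to wait and no grade to recover to. Section 2.1.3 names diarrhea as one of the two major dose-limiting toxicities of irinotecan, so this is one of the places where the table most needs to be clear. What is at stake is patient safety and consistent dosing.

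**Working it through.** The plan states no figure on this point, so the check compares the text and adds a small dose calculation.

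**Step 1. The two readings for a first grade 3-4 episode of diarrhea or mucositis at full dose.**

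| State on the next Day 1 | Read by the column heading | Read by the introductory sentence |
|---|---|---|
| Cleared (below grade 2) | No row applies; full doses repeat | Irinotecan and infusional 5-FU one level down, bolus dropped |
| Still grade 3-4 | One level down, bolus dropped, no hold | One level down, bolus dropped, no hold |

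The readings differ in the first line only. The missing hold is in the second line and is common to both.

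**Step 2. Size of the difference in the first line, per cycle.** The dose levels are those in the Section 6.2.2 table: irinotecan 180 mg/m2 initially and 150 at level -1; 5-FU bolus 400 initially; 5-FU infusion 2400 initially and 1920 at level -1.

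- Irinotecan: 180 − 150 = 30 mg/m2; 30/180 = 16.7% lower by the introductory sentence.
- Total 5-FU by the heading: 400 + 2400 = 2800 mg/m2.
- Total 5-FU by the introductory sentence: 0 + 1920 = 1920 mg/m2.
- Difference: 880 mg/m2; 880/2800 = 31.4% lower.
- Oxaliplatin: 85 mg/m2 under both.

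**Step 3. Is the missing hold a pattern in the protocol or an exception?**

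- Same table, grade 3-4 nausea/vomiting: all therapy held until grade 2 or less.
- Section 6.2.2.1, grade 2-4 neutropenia: all therapy held until the neutrophil count is at least 1500.
- Section 6.2.2.1, grade 2-4 thrombocytopenia: all therapy held until platelets exceed 100K.
- Section 6.2.3: "Capecitabine will be held for any Grade 3 or 4 toxicity", resuming after recovery to grade 1 or less.
- Neurotoxicity rules: where no hold is wanted the text says so outright for oxaliplatin, and it separates toxicity that resolves between treatments from toxicity that persists.

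Of the three grade 3-4 rows in the non-hematologic table, one has a hold and a recovery grade and two have neither. Those two rows neither hold nor say that no hold is intended. No recovery grade for FOLFIRINOX diarrhea or mucositis appears elsewhere in the document.

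**Step 4. Does the primary analysis depend on this?** Section 14 counts R0 resections among all patients who start induction chemotherapy and requires at least 9 of 50. The dose-reduction rules enter neither the count nor the denominator, so the stated 91% power and 6% type I error are unchanged.

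**The case against.** The best reply is that the sentence and the heading can be reconciled. The sentence says which toxicity counts, and the heading says when the dosing decision is made. The sentence stands just before the table. The Section 9 calendar schedules toxicity assessment every other week after cycle 1, which matches the 14-day cycle, and Section 11.2 includes events found by questioning. An oncologist on Day 1 would ask about the past two weeks. That reading is the likelier one. It does not remove the conflict in wording, and it supplies no recovery grade.

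The second reply is that a hold is already available, through the delay clause, the oncologist's discretion and the status of the rules as recommendations. This also stands, and most oncologists would probably wait. A reader might infer that the protocol obliges sites to treat through active grade 3-4 diarrhea; these clauses show that it does not. They permit a hold, however, without requiring one or saying when to resume.

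A reader might also infer that the heading would miss the usual episode of irinotecan diarrhea. Section 2.1.3 says "Diarrhea can occur either acutely (within the first 24 hours) and delayed (after 2-4 days" and gives a usual duration of 5-7 days, so adding the two suggests recovery before the next Day 1. The documents do not support that step. The same section ties delayed diarrhea to the second or third weekly dose, whereas this trial doses every 14 days, and the duration follows a remark about grade IV diarrhea.

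**Conclusion.** The point holds as a limited safety and clarity defect. The table carries two grading times that disagree for an episode cleared by Day 1, by 17% of irinotecan and 31% of total 5-FU in the next cycle. Those figures assume a first event at full dose and a clinician who follows the heading alone. Under either reading, two of the three grade 3-4 rows lack a hold and a recovery grade.

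How many patients this would touch cannot be derived. Section 6.1.1.2 gives grade 3/4 diarrhea in 12.7% of FOLFIRINOX patients in the cited phase III trial, and 0.127 × 50 = 6.35, or about 6 patients. That is a sense of scale, not a bound in either direction. That trial planned six months of therapy against eight 14-day cycles here, and it tested FOLFIRINOX without the losartan added here, for which Section 2.1.5 lists diarrhea among reactions above 10% incidence. The documents give no rate for diarrhea or mucositis still at grade 3-4 on Day 1, so the number exposed to the missing hold could be anywhere from none to all of those affected.

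The correction is worth making because it costs almost nothing. It has no bearing on the design figures or the primary conclusion.

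**What to change.** Make two edits to the Section 6.2.2.2 table:

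1. Change the first column heading to *Worst non-hematologic toxicity since the previous Day 1, including any present on Day 1*. This keeps the rule in the introductory sentence and also covers toxicity still active at the visit. It settles the grading time for the grade 2 rows too.
2. In the grade 3-4 diarrhea and mucositis rows, insert *HOLD ALL THERAPY until G2 or less, then:* before the existing entries, which stay as they are. This matches the nausea/vomiting row. For a patient already recovered by Day 1 the condition is met and nothing is delayed. The clinical team may prefer grade 1 or less, the threshold Section 6.2.3 uses for capecitabine.

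The cost is one heading and one phrase in two rows, made by amendment. Dose levels, visits, sample size and the oncologist's discretion do not change. The downside is a short cycle delay for the few patients whose grade 3-4 diarrhea or mucositis is unresolved on Day 1.
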